4.3.3 Exhaled Breath Volatile Data Generation and Metabolomic Analysis

Unbiased metabolomics analysis of bio-volatiles and biofluids has the potential to identify 100-1000's of metabolites in any single sample. Our

A PILOT STUDY OF EXHALED BREATH ANALYSIS TO ASSESS PNEUMONITIS
DEVELOPMENT AFTER CHEMORADIOTHERAPY FOR STAGE III NSCLC
Wake Forest Baptist Comprehensive Cancer Center (WFBCCC)
WFBCCC 98119

group has successfully assessed bio-volatiles and biofluids by unbiased metabolomics (30, 31). Although there is no single method that allows for the complete analysis of the metabolite, utilizing multiple modes of sample preparation and analysis will potentially identify a number of classes of compounds relevant to this study. The bio-volatile that will potentially be identified are various hydrocarbons, aldehydes, ketones, and alcohols.

Exhaled breath samples will be analyzed using a Markes thermal desorber, TD100-xr, to inject breath samples onto an Agilent two-dimensional GC system 7890B in tandem with LECO's Pegasus 4D Time-of-Flight instrument system (TD-GCxGC-TOFMS). The collected spectra will be processed using LECO's ChromaTOF version 4.72 software. Initial data processing includes peak deconvolution, 1st and 2nd dimension retention time recordings, signal to noise ratio calculation, unique mass detection, peak area determination, and compound identification based on the spectral pattern similarity match against established mass spectral reference libraries (NIST17, 2017 National Institute of Standard Technology, NIH, USA). Identified spectral matches will be aligned using R-program R2DGC (32) to determine common metabolites in patients prior to and after CRT. MetaboAnalyst 4.0 will be employed to normalize and transform the data for univariate and multivariate statistical analysis (33). Additional statistical analysis may be performed using Graphpad Prism 8 (Graphpad Software, Inc).

4.3.4 Data Storage

All research data collected on this study will be stored on Wake Forest Baptist Medical Center password protected computers and servers.

5.0 Study Outcomes and Outcome Measures

5.1 Primary Outcome

5.1.1 Concentrations of TGF- β 1, IL-6, IL-1 α , and IL-10 (ng/mL) measured in exhaled breath condensate prior to CRT (baseline), at 2 weeks after CRT start, 6-weeks after CRT start (the end of CRT), and 1 month after completion of CRT.

5.2 Secondary Outcomes

5.2.1 Concentrations of TGF- β 1, IL-6, IL-1 α , and IL-10 (ng/mL) measured in exhaled breath condensate prior to CRT (baseline), at 2 weeks after CRT start, 6-weeks after CRT start (the end of CRT), and 1

A PILOT STUDY OF EXHALED BREATH ANALYSIS TO ASSESS PNEUMONITIS
DEVELOPMENT AFTER CHEMORADIOTHERAPY FOR STAGE III NSCLC
Wake Forest Baptist Comprehensive Cancer Center (WFBCCC)
WFBCCC 98119

month after completion of CRT compared among patients who develop SP versus those who do not. SP will be assessed at each time point and will be defined as presence of CTCAE version 5.0 grade 2 or higher SP (Appendix C).

- 5.2.2 Concentration of TGF- β 1, IL-6, IL-1 α , and IL-10 (ng/mL) measured in serum prior to CRT (baseline), at 2 weeks after CRT start, 6-weeks after CRT start (the end of CRT), and 1 month after completion of CRT:
 - 5.2.2.1 Compared to concentrations of same biomarkers measured in exhaled breath condensate at same time points (see 5.2.1);
 - 5.2.2.2 and compared among patients who develop SP versus those who do not.
- 5.2.3 Microbial signatures measured in exhaled breath condensate prior to CRT, and presence/absence of SP at study end.

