6.0 Analytic Plan

6.1 Analysis of Primary Outcome, Sample Size, and Power

This is a pilot study; therefore, our objectives are exploratory in nature, and we have little to no pre-existing findings reported in the literature to guide our expectations. With this in mind, we plan to recruit a single cohort of 50 patients. In order to be able to examine the questions concerning intra-person variability in biomarker measures over time, and the possible relationships of breath and microbial biomarker signatures with lung cancer outcomes, both pre- and post-radiation treatment measures are needed on each participant. Our goal is to

A PILOT STUDY OF EXHALED BREATH ANALYSIS TO ASSESS PNEUMONITIS
DEVELOPMENT AFTER CHEMORADIOTHERAPY FOR STAGE III NSCLC
Wake Forest Baptist Comprehensive Cancer Center (WFBCCC)
WFBCCC 98119

collect from each patient one pre- (T0) and two post-treatment (T1, immediately post treatment and T2, one month following completion of treatment) samples of breath and serum to be examined. Our target sample size of 50 patients is the target for patients with pre- and post- samples collected. Our main interest is in differences between biomarker levels at T1-T0, where we expect to see the largest differences.

First, for the primary objective of detecting intra-person variability from T1 to T0 in EBC measures, the table below shows different power levels for n=50 patients, using a 2-tailed alpha of 0.05.

Detectable standard deviation units	Power
0.3	0.55
0.4	0.79
0.5	0.93

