6.2 Analysis of Secondary Outcomes

To examine the association between differences in pre-treatment and post-treatment EBC concentrations of biomarkers and development of SP, we will conduct 2-group independent t-tests comparing mean change levels (from T0 to T1) in each marker among those who developed SP (expected to be around 10-15 patients) to those who remained free of SP at the study end. We will also conduct various exploratory logistic regression models, if numbers permit, to predict the outcome of SP, using various biomarker values (e.g., T0, difference between T0 and T1, etc.) as key predictors. If numbers permit, we will also examine results from repeated measures logistic regression models, using the three repeated measures of the biomarkers as predictors, and/or using at least one delta score as a predictor. Our goal in such exploratory modeling will be to discern what time points or what differences in EBC biomarkers appear to be most highly predictive of occurrence of SP. We will conduct most of this modeling on a single biomarker at a time; based on biological rationale, bivariate findings, and numbers, we may also explore some modeling where more than one biomarker is included.

We also wish to determine to what degree serum levels of biomarkers correlate with levels of the same biomarkers measured in exhaled breath condensate, and how well these serum markers predict SP. For this latter goal, we will use a similar plan as described in the preceding paragraph.

For the former objective (examining how well serum and breath levels of biomarkers correspond), because we do not hypothesize a priori that these 2 different sources of a biomarker are actually measuring (estimating) the same quantity for any of the markers, we do not expect absolute agreement. We will

A PILOT STUDY OF EXHALED BREATH ANALYSIS TO ASSESS PNEUMONITIS
DEVELOPMENT AFTER CHEMORADIOTHERAPY FOR STAGE III NSCLC
Wake Forest Baptist Comprehensive Cancer Center (WFBCCC)
WFBCCC 98119

thus first examine scatterplots of the serum vs breath measure of each biomarker, and if the association appears monotonic in the scatterplot, we will compute Spearman rank correlations. (If the association appears linear and monotonic, we will compute Pearson correlations.) If an association between a serum and breath measure of a biomarker is non-monotonic, we will attempt to fit a curve describing the association most accurately.

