7.3 Study Calendar

	Prior to CRT Start	2-week after CRT Start^e	6-week after CRT Start^e	1 Month after CRT End^e	4 Months after CRT End^e
Informed consent	X				
Demographics	X				
Medical history (Appendix E)	X				
Physical Exam	X				
Pulmonary Function Tests (Appendix H)	X ⁱ				
Antibiotic and Steroid Use (Appendix D)	X	X ^e	X ^e	X ^g	X ^g
Smoking Status (Appendix G)	X	X ^e	X ^e	X ^g	X ^g
Breath Collection (EBC ^a /EBV ^{b,h})	X ^d	X ^e	X ^e	X ^g	
Blood collection ^c	X ^d	X ^e	X ^e	X ^g	
CT chest with or without contrast	X				X ^g
Pneumonitis Evaluation (Appendix C)	X			X ^g	X ^g
Dietary Evaluation (Appendix M)	X ^d	X ^e	X ^e	X ^g	
Radiotherapy Detail Form (Appendix I)	X ^f				

^a Approximately 1-1.5 mL of EBC will be generated in 10 min of breathing

^b 500 ml of EBV in each of 4 collection tubes will be collected in 5-7 min of breathing

^c Blood sample in each redtop (x1) and purpletop (x1) vacutainer blood collection tube

^d Pre-CRT sample collections to occur within 14 days of the date of RT start. It is recommended but not required that this occurs on the date of CT simulation.

^e May occur within +/- 7 days of the scheduled time point measured from the date of RT start. The 2-week after CRT start, 6-week after CRT start, and 1-month after CRT time points will be coordinated with routine blood draws through medical oncology by the study research nurse.

^f To be completed after completion of treatment planning. This may also be completed at any time after CRT has started.

^g May occur within +/- 14 days of the scheduled time point measured from the date of RT end.

^h EBV collection is optional, as defined in Section 4.2.2.

ⁱ Pulmonary function tests must have occurred within 1 year of CRT Start. Results of testing performed at Wake Forest sites or other outside facilities is acceptable.

A PILOT STUDY OF EXHALED BREATH ANALYSIS TO ASSESS PNEUMONITIS
DEVELOPMENT AFTER CHEMORADIOTHERAPY FOR STAGE III NSCLC
Wake Forest Baptist Comprehensive Cancer Center (WFBCCC)
WFBCCC 98119

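### Section 6.2 models symptomatic pneumonitis on the T2 biomarker sample without requiring onset after T2; separately, 5.2.1 and the 7.3 calendar disagree on when pneumonitis is assessed

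*Combined protocol and SAP*

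**What the plan says.** **Outcome.** Section 5.2.1 lists four biomarker time points (baseline, 2 weeks and 6 weeks after the start of chemoradiotherapy (CRT), and 1 month after its end). It then says: "SP will be assessed at each time point and will be defined as presence of CTCAE version 5.0 grade 2 or higher SP".

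**Calendar.** In section 7.3 the row "Pneumonitis Evaluation (Appendix C") is marked before CRT, at 1 month and at 4 months after CRT. The 2-week and 6-week cells are blank, although breath, blood, diet, smoking and antibiotic/steroid use are all marked there. The 1-month and 4-month marks may fall "within +/- 14 days of the scheduled time point measured from the date of RT end".

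**Samples analysed.** Section 6.1 works with three: T0 before treatment, T1 immediately after it, and "T2, one month following completion of treatment". Section 7.2 has serum and breath condensate collected at the same 1-month visit as the clinical assessment.

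**Analysis.** Section 6.2 first plans t-tests "comparing mean change levels (from T0 to T1) in each marker among those who developed SP (expected to be around 10-15 patients") with patients still free of SP at study end. Subject to numbers, it then allows repeated-measures logistic models "using the three repeated measures of the biomarkers as predictors, and/or using at least one delta score as a predictor". The aim of the exploratory modelling is to "discern what time points or what differences in EBC biomarkers appear to be most highly predictive of occurrence of SP". A similar plan applies to serum markers and SP. No text sets an order in time between SP onset and the predictor sample.

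**The concern.** The study looks for markers that identify patients at risk of SP, so that preventive measures could be studied (section 1.0). A marker that rises only once a patient is symptomatic does not serve that aim. Section 6.2 classifies patients by SP at any time up to study end and lets T0, T1 and T2 compete as predictors. A patient already in SP at the 1-month visit would supply a T2 value measured during the event, and the model would count it as a prediction of that event. Corticosteroid treatment of SP, which section 1.0 describes, could also alter that value. T2 might then look like the best time point because it reflects disease already present.

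The mismatch between 5.2.1 and 7.3 is a separate and smaller matter. Staff following the calendar would not deliver the assessments that 5.2.1 describes, and SP already present at T1 would not be graded on the study form at that visit.

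**Working it through.** **1. Schedules side by side**

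| Time point | SP assessed per 5.2.1 | SP evaluation in 7.3 | Breath and blood in 7.3 |
|---|---|---|---|
| Baseline (T0) | yes | yes | yes |
| 2 weeks | yes | blank | yes |
| 6 weeks (T1) | yes | blank | yes |
| 1 month after CRT (T2) | yes | yes | yes |
| 4 months after CRT | not listed | yes | blank |

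Two of the four time points in 5.2.1 have no evaluation. The blanks do not look like an extraction fault: the last two marks in the row carry the footnote that counts from the end of radiotherapy, which fits the 1-month and 4-month columns. At T2, the sample and the evaluation share a visit, so SP status at T2 is already due to be recorded.

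**2. Can SP precede T2?**

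One month is 30.4 days, or 4.3 weeks. With the ±14-day window, T2 falls 4.3 − 2 = 2.3 to 4.3 + 2 = 6.3 weeks after radiotherapy ends. Section 1.0 places radiation pneumonitis within several weeks to months of CRT, so onset before T2 is possible. Section 8.0 ties the 1-month visit to confirming eligibility for consolidation immunotherapy. SP caused by immunotherapy therefore cannot precede T1 and should mostly follow T2. The documents give no onset times, so the number of cases present at T2 cannot be calculated.

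**3. Check of method against the plan's own table**

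Section 6.1 gives power 0.55, 0.79 and 0.93 for changes of 0.3, 0.4 and 0.5 SD with n = 50 and two-sided 5%. A paired t-test (noncentral t, 49 df) gives 0.548, 0.792 and 0.934. The table is reproduced. It concerns the primary outcome and is not affected by this point.

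**4. Cost of excluding cases already in SP**

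Expected SP cases: 50 × 0.15 = 7.5 to 50 × 0.20 = 10 from section 2.0, and 10 to 15 from section 6.2, so about 8 to 15. A two-group t-test on one marker stands in here for a single-marker logistic model. With group sizes n1 and n2, the noncentrality is d × √(n1·n2/(n1+n2)) on n1+n2−2 df, solved for d at 80% power and two-sided 5%. For 10 vs 40, √(400/50) = 2.83 and d = 1.01.

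| SP cases in total | Assumed in SP by T2 | Groups compared | Detectable difference (SD) |
|---|---|---|---|
| 10 | 0 | 10 vs 40 | 1.01 |
| 10 | 1 | 9 vs 40 | 1.06 |
| 10 | 2 | 8 vs 40 | 1.11 |
| 10 | 5 | 5 vs 40 | 1.36 |
| 8 | 0 | 8 vs 42 | 1.10 |
| 8 | 4 | 4 vs 42 | 1.50 |
| 15 | 0 | 15 vs 35 | 0.88 |
| 15 | 8 | 7 vs 35 | 1.19 |

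The second column is assumed throughout. One case is 1/15 = 6.7% to 1/8 = 12.5% of the SP group; that is the weight of a single case, not an estimate of how many are affected.

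**The case against.** The strongest reply is that this is a pilot whose objective 2.2.1 asks only for associations, that section 6.1 puts the main interest in T1 minus T0, and that the models in question are exploratory and depend on numbers. All of that stands, and it limits the point to interpretation. It does not remove it, because the stated goal of those models is to rank time points by how well they predict SP.

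It can also be said that 5.2.1 is loosely worded. Its list omits the 4-month visit, where SP is plainly assessed, and section 7.2 takes SP from routine follow-up after CRT, as the calendar does. That is a fair reading, and correcting 5.2.1 alone would settle the inconsistency.

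Weekly on-treatment visits (7.1) and the record of steroid use at every calendar point may reveal early SP, but neither is a specified CTCAE grading. Appendix C is not in the available text and may already hold an onset date. That would help apply an ordering rule, but would not put one in section 6.2.

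A reader might infer that the blank 2-week and 6-week cells cause the problem at T2. They do not: the 1-month evaluation already covers T2, and extra forms would help only at T1, where the number of affected cases may be zero.

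**Conclusion.** The point holds as a minor one. Followed as written, section 6.2 lets SP already present at the 1-month visit count as predicted by the T2 sample, and 5.2.1 does not match 7.3 at 2 and 6 weeks.

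Stronger readings are not supported:

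- A reader might infer that the T0-T1 comparison is invalid. It remains a valid association, and the documents do not show that any SP begins by week 6.
- A reader might infer that SP cases are being missed. Nothing shows that the final SP count changes, since the 1-month and 4-month evaluations stay in place.
- A reader might infer that T2 will necessarily come out as the best predictor. Without onset times, neither the number of prevalent cases nor the direction of any distortion can be established.

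The primary outcome and the serum-breath comparison (2.2.2.1) are unaffected. The conclusion assumes that the calendar row is as printed and that no ordering rule sits in an appendix that is not available here.

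**What to change.** **Main change, section 6.2.** State that any model using T2, or a change score involving T2, as a predictor is also run without patients who had grade 2 or higher SP at or before the T2 sample, using the 1-month evaluation already scheduled. Only SP arising after T2 supports a predictive reading; models that include prevalent cases are reported as associations. Because serum follows a similar plan, the sentence should cover both breath and serum models.

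*Cost:* one sentence and no new procedure, but fewer SP cases in that analysis. The loss is small if one case is excluded (1.01 to 1.06 SD at 10 vs 40) and substantial if five are (1.36 SD). Keeping the full-cohort model beside it limits the damage.

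**Secondary change, 5.2.1 or 7.3.** Choose one:

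- Mark the pneumonitis form at the existing 2-week and 6-week visits, with onset date if Appendix C lacks it. This adds one form at two visits and allows the same check at T1.
- Correct 5.2.1 to baseline, 1 month and 4 months. This adds no procedure, but leaves SP status at T1 without a study grading.

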5.3 Exploratory Outcome

- 5.3.1 Metabolomic signatures associated with the development of SP. This will include quantitative assessments of metabolic characteristics measured at prior to CRT (baseline), at 2 weeks after CRT start, 6-weeks after CRT start (the end of CRT), and 1 month after completion of CRT. Quantitative assessments of metabolomic assessments measured prior to CRT. Using these three sets of quantitative assessments (at each of the three time points), "signatures" will be developed (described in statistical analysis section) and compared to see whether there are characteristics that remain similar or change when comparing SP and no-SP measures.

6.0 Analytic Plan

6.1 Analysis of Primary Outcome, Sample Size, and Power

This is a pilot study; therefore, our objectives are exploratory in nature, and we have little to no pre-existing findings reported in the literature to guide our expectations. With this in mind, we plan to recruit a single cohort of 50 patients. In order to be able to examine the questions concerning intra-person variability in biomarker measures over time, and the possible relationships of breath and microbial biomarker signatures with lung cancer outcomes, both pre- and post-radiation treatment measures are needed on each participant. Our goal is to

A PILOT STUDY OF EXHALED BREATH ANALYSIS TO ASSESS PNEUMONITIS
DEVELOPMENT AFTER CHEMORADIOTHERAPY FOR STAGE III NSCLC
Wake Forest Baptist Comprehensive Cancer Center (WFBCCC)
WFBCCC 98119

collect from each patient one pre- (T0) and two post-treatment (T1, immediately post treatment and T2, one month following completion of treatment) samples of breath and serum to be examined. Our target sample size of 50 patients is the target for patients with pre- and post- samples collected. Our main interest is in differences between biomarker levels at T1-T0, where we expect to see the largest differences.

First, for the primary objective of detecting intra-person variability from T1 to T0 in EBC measures, the table below shows different power levels for n=50 patients, using a 2-tailed alpha of 0.05.

Detectable standard deviation units	Power
0.3	0.55
0.4	0.79
0.5	0.93

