4.2 Data Collection Methods

4.2.1 Clinical Data Collection

Implementation of this prospective observational pilot study has the full support of the Wake Forest Thoracic Multidisciplinary Research Committee. We plan to enroll 50 patients with newly diagnosed locally advanced non-

A PILOT STUDY OF EXHALED BREATH ANALYSIS TO ASSESS PNEUMONITIS
DEVELOPMENT AFTER CHEMORADIOTHERAPY FOR STAGE III NSCLC
Wake Forest Baptist Comprehensive Cancer Center (WFBCCC)
WFBCCC 98119

small cell lung cancer undergoing standard of care chemoradiotherapy. Baseline characteristics including demographics (age, sex, ethnicity, and race), tobacco use history, past medical history (COPD, interstitial lung disease, asthma, etc.), antibiotic and steroid use, and oncologic history (TNM stage, tumor size, location, histology and date of diagnosis) will be recorded. Baseline pulmonary function, tested as a part of routine pre-treatment workup, will be collected if available. Treatment-related factors will be recorded including radiotherapeutic modality (3D conformal radiotherapy, intensity-modulated radiotherapy, or volumetric modulated radiotherapy), detailed volumetric and dosimetric parameters for each patient's individualized radiation plan, as well as type of chemotherapy and immunotherapy used.

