6.5 Length of Study

In order to accrue 50 patients at a rate specified above, the length of the accrual will be approximately 2 years. The study will complete after the 4-month follow-up of the last patient and we estimate the total duration at no longer than 2.5 years.

A PILOT STUDY OF EXHALED BREATH ANALYSIS TO ASSESS PNEUMONITIS
DEVELOPMENT AFTER CHEMORADIOTHERAPY FOR STAGE III NSCLC
Wake Forest Baptist Comprehensive Cancer Center (WFBCCC)
WFBCCC 98119

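### Section 6.1 powers the study on 50 complete pre/post pairs, but enrolment and timeline are also set at 50, with no allowance for loss

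*Combined protocol and SAP*

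**What the plan says.** Section 6.1 uses the number 50 in two senses. It first says "we plan to recruit a single cohort of 50 patients". A few sentences later it says "Our target sample size of 50 patients is the target for patients with pre- and post- samples collected". The power statement "for the primary objective of detecting intra-person variability from T1 to T0 in EBC measures" then continues with "the table below shows different power levels for n=50 patients, using a 2-tailed alpha of 0.05". The table gives power of 0.55, 0.79 and 0.93 at 0.3, 0.4 and 0.5 standard deviation units.

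The operational sections use 50 as the number entering the study:

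- Section 4.2.1: "We plan to enroll 50 patients with newly diagnosed locally advanced" disease.
- Section 3.3 takes 44% of 50 to project about 22 women enrolled.
- Section 6.5 bases roughly 2 years of accrual on 50 patients and adds "we estimate the total duration at no longer than 2.5 years".

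Section 6.4 expects about 2 patients per month. That rate is already reduced for eligible patients who do not enrol, but not for anything that happens after enrolment. No section gives an attrition rate, an allowance for unusable samples, an over-enrolment figure or a replacement rule.

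**The concern.** A T1-T0 difference exists only for a patient with a usable sample at both times. The number enrolled and the number of pairs are equal only if nobody is lost in between.

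The protocol leaves room for loss. Section 3.1 admits patients with suspected stage III disease on the basis of a treatment plan. Registration comes before chemoradiotherapy (CRT). T1 falls about 6 weeks after CRT starts. Each collection yields about 1-1.5 mL of exhaled breath condensate (EBC) according to the study calendar. That volume must serve triplicate assays of four markers (Section 4.3.1), and the pre-treatment sample must also serve the microbiome work. None of this shows that loss will be large, but it does mean that zero loss is an unstated assumption.

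At stake is whether the primary power figures and the enrolment and duration figures can both be met. With appreciable loss, one set has to give way.

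**Working it through.** **Inputs from the documents.** Two-sided alpha of 0.05, n = 50, effects of 0.3/0.4/0.5 SD and stated power of 0.55/0.79/0.93 (Section 6.1); accrual of about 2 per month (6.4); accrual of about 2 years and a total of at most 2.5 years, or 30 months (6.5); end of CRT at about 6 weeks (5.1.1); last visit about 4 months after CRT ends (7.2, 7.3).

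**Assumed.** Loss of 5% to 20% between enrolment and a usable T0-T1 pair, because the documents give no figure. Six weeks of CRT is taken as about 1.5 months.

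**Step 1: reproduce the table.** Paired t-test power comes from the noncentral t distribution with n - 1 degrees of freedom and noncentrality d × √n. For n = 50, √50 = 7.071, so the noncentralities are 2.12, 2.83 and 3.54. Power is 0.548/0.792/0.934, which matches the stated figures. A one-sided test (0.673/0.874/0.967) and a two-sample test with 50 per group (0.323/0.516/0.705) do not match. The table is therefore a two-sided calculation on 50 complete pairs.

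**Step 2: hold enrolment at 50 and let pairs fall.** Same formula:

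| Pairs | Loss | 0.3 SD | 0.4 SD | 0.5 SD |
|---|---|---|---|---|
| 50 | none | 0.55 | 0.79 | 0.93 |
| 49 | 1 patient | 0.54 | 0.78 | 0.93 |
| 48 | 2 patients | 0.53 | 0.77 | 0.92 |
| 47 | about 5% | 0.52 | 0.77 | 0.92 |
| 45 | 10% | 0.50 | 0.75 | 0.91 |
| 40 | 20% | 0.46 | 0.69 | 0.87 |

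**Step 3: hold pairs at 50 and let enrolment rise.** Enrolment = 50 / (1 - loss), rounded up. Accrual = enrolment / 2 months. Total = accrual + 1.5 + 4 months.

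| Loss | Enrol | Accrual (months) | Total (months) |
|---|---|---|---|
| 5% | 50/0.95 → 53 | 26.5 | 32 |
| 10% | 50/0.90 → 56 | 28 | 33.5 |
| 15% | 50/0.85 → 59 | 29.5 | 35 |
| 20% | 50/0.80 → 63 | 31.5 | 37 |

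**Step 4: how much slack the 30 months holds.** With no loss and exactly 2 per month, the total is 50/2 + 1.5 + 4 = 30.5 months. With the protocol's own round figure of 2 years for accrual, it is 24 + 1.5 + 4 = 29.5 months. If follow-up is counted leniently as 4 months from the last enrolment, the total is 25 + 4 = 29 months. On that count at most (30 - 4) × 2 = 52 patients fit, which covers a loss of 2/52, about 4%.

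**The case against.** The strongest reply is that Section 6.1 settles the meaning: 50 is explicitly the target for complete pairs, and the table follows from it. That stands as far as the power calculation goes. A reader might infer that the table is miscalculated, and the documents do not support that. But the reply moves the problem without removing it, because Sections 3.3, 4.2.1 and 6.5, and the recruitment sentence in 6.1 itself, then carry a number with no margin.

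A second reply is that loss may be small. Patients must be willing and able to give breath samples, T1 is only about six weeks after CRT starts, and breath is collected on the days of routine blood draws. That is fair. The 10% and 20% rows are scenarios, not forecasts. A reader might infer that any attrition at all spoils the stated figures. In practice 48 or 49 pairs keep power within 2 points of the table.

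A reader might also infer from the 30.5 months in Step 4 that the 2.5-year limit is broken even with no loss. The documents do not support that either. The accrual rate and accrual period are given as approximate and the total as an estimate, and the 2-year figure brings the total to 29.5 months. The fair statement is that there is little or no slack.

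Finally, this is a pilot that describes its objectives as exploratory. The table designates no effect size as the target, and no go/no-go decision rests on it. That limits the consequence, but the protocol still presents power for its primary objective and a maximum duration, and the two should be compatible.

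**Conclusion.** The point holds as an inconsistency between the number enrolled and the number evaluable. The power table is right for 50 pairs, but a plan to enrol 50 reaches it only with essentially no loss. The effect becomes material from about 5-10% loss. At 0.4 SD, power goes from 0.79 to about 0.75 at 10% loss and 0.69 at 20%. Alternatively, 3 to 13 more patients are needed at 5-20% loss, and the study runs about 32 to 37 months instead of at most 30. These sizes rest on assumed loss rates, a two-sided paired t-test, accrual of about 2 per month, and a duration that counts about 6 weeks of CRT plus 4 months of follow-up. The importance is moderate: it should be corrected, but it does not undermine the study.

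**What to change.** State two numbers separately throughout: patients to enrol, and patients evaluable with usable T0 and T1 EBC. Give the assumed loss or a replacement rule that links them. Then choose one of two courses.

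(a) Keep the Section 6.1 target of 50 pairs. Say that accrual continues until 50 pairs exist, and restate the enrolment figures in 3.3, 4.2.1 and 6.1 and the timeline in 6.5. This follows the protocol's own definition. At 5-20% loss it costs about 3 to 13 further patients and 1.5 to 6.5 further months of accrual at 2 per month.

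(b) If enrolment is capped at 50, reword the target sentence in 6.1 and restate the power table for the expected number of evaluable pairs, for example 45 and 40. This needs no extra patients or time. Its cost is a slightly less favourable stated power.
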